Official Title of the study: Evaluation of the Effects of Computer-Controlled and Traditional Local Anesthesia on Pain and Anxiety in Children With Molar Incisor Hypomineralization

Organization's Unique Protocol ID: 23-KAEK-205

NCT number: Not available

Date of the document: 14.09.2023

Evaluation of the Effects of Computer-Controlled and Traditional Local Anesthesia on Pain and Anxiety in Children With Molar Incisor Hypomineralization

Materials and Methods

Ethics Approval: Ethical approval for this study was obtained from the Tokat Gaziosmanpaşa University Faculty of Medicine Clinical Research Ethics Committee (Approval No: 16-01 / Date: 14.09.2023). The study was conducted in accordance with the principles of the Declaration of Helsinki. Before the procedures, detailed information about the study's purpose and the treatment to be performed was provided to the children and their parents, and both the child assent and informed consent forms were obtained.

Determination of Sample Size: Using G*Power v.3.1.9.7, a power analysis for the planned study with 2 dependent groups indicated that, with 80% test power ($1-\beta$) and an effect size of 0.56, 28 patients (56 permanent first molars) were planned to be included (Smail-Faugeron et al., 2019).

Participant Selection Criteria: The study included 28 children aged between 6 and 12 years who met the following criteria: absence of systemic disease; a score of 3 or 4 on the Frankl Behavior Rating Scale; bilateral MIH in the maxilla or mandible; deep dentin caries in the permanent first molars that could be treated with vital pulp therapy; and no history of acute pain.

Study Design: The study was conducted using a split-mouth design with 28 patients and 56 teeth who met the inclusion criteria and were recruited from the Department of Pediatric Dentistry, Faculty of Dentistry, Tokat Gaziosmanpaşa University. The patients included in the study were randomly assigned to two groups:

- **Control group:** Anesthesia administered using the conventional injection technique.
- **Study group:** Intraosseous anesthesia administered with the computer-controlled anesthesia device (SleeperOne).

Teeth affected by MIH were classified according to the Molar–Incisor Hypomineralization Treatment Need Index (MIH-TNI). Those in category 2 were evaluated as “Without hypersensitivity,” while those in category 4 were assessed as “With hypersensitivity” (Figure 1).

Dental Anesthesia Methods: All procedures were performed by the same dentist in a single-unit room, and appointments were scheduled as the first of the morning (08:15). Patients were instructed to arrive with a full stomach and brushed teeth. Before the procedure, all steps were explained using the tell–show–do technique.

All treatments were planned in two sessions, scheduled 7–10 days apart. The anesthesia method to be used in the first session was determined by randomization. For this purpose, each patient was asked to randomly select one of the envelopes labeled with different anesthesia methods. In addition, to determine which tooth to begin treatment on, patients were asked to choose between blue and green cards: children who selected the blue card started with the right first molar, while those who selected the green card started with the left first molar.

In both the control and study groups, a topical anesthetic spray containing 10% lidocaine (Vemcaine® pump spray 10%, Vem Pharmaceutical Industry and Trade Co., Türkiye) was applied to the target area with a cotton pellet for 1 minute before anesthesia administration. In the control group, anesthesia was administered using a 2 ml plastic dental syringe (Berika Technology Medical Manufacturing Import Export Trade Co., Türkiye) for both infiltration and mandibular block

anesthesia. For the maxillary teeth, buccal infiltration anesthesia was administered; for the mandibular teeth, mandibular block anesthesia was administered. In the study group, anesthesia was performed using a computer-controlled local anesthesia system with 30-gauge, 9 mm Effitec extra-short needles (Dental Hi Tec, [name], France). Following topical anesthesia, half of a carpule of local anesthetic solution (Ultracaine D-S Fort, Sanofi Aventis Deutschland, Frankfurt, Germany) was administered to the designated teeth using the intraosseous anesthesia technique, in accordance with the manufacturer's instructions.

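### Does changing device and injection route together, against a control that differs by jaw, call for a change to the plan?

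*Combined protocol and SAP*

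**What the plan says.** The title presents the contrast as "Evaluation of the Effects of Computer-Controlled and Traditional Local Anesthesia on Pain and Anxiety in Children With Molar Incisor Hypomineralization". Under Study Design the study condition is "Intraosseous anesthesia administered with the computer-controlled anesthesia device (SleeperOne" and the control condition is "Anesthesia administered using the conventional injection technique".

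Dental Anesthesia Methods gives the detail. The control device is a manual syringe ("In the control group, anesthesia was administered using a 2 ml plastic dental syringe"), and the control route depends on the jaw: "For the maxillary teeth, buccal infiltration anesthesia was administered; for the mandibular teeth, mandibular block anesthesia was administered". Every study tooth is treated by the intraosseous route. Each child receives both methods in two sessions, and "The anesthesia method to be used in the first session was determined by randomization".

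Eligibility requires "bilateral MIH in the maxilla or mandible". The two treated teeth are a right and a left first molar, so I read both as lying in the same jaw.

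The sample size rests on one figure: "an effect size of 0.56, 28 patients (56 permanent first molars) were planned to be included". The Statistical Analysis section lists tests but names no jaw term, stratification or per-jaw summary. The document has no aims or conclusion section and names no primary pain outcome or time point.

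**The concern.** The title names one factor, computer control, but two factors differ between the arms. No control tooth receives an intraosseous injection, and no study tooth receives infiltration or block. A reader who sees less pain in the study condition could credit the device when the route would explain the result equally well. Enrolling more children would not help, because the two factors are perfectly aligned.

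The second worry is the comparator. If both jaws are enrolled, the overall difference averages intraosseous versus infiltration and intraosseous versus block, with weights set by however many children fall in each jaw. Without the counts, a reader cannot tell which of the two the result mainly describes.

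**Working it through.** **1. The planned size.** Inputs: effect size 0.56 and power 80% with two dependent groups (Determination of Sample Size), and a 0.05 significance level (Statistical Analysis). I assume a two-sided test and read 0.56 as the mean within-child difference divided by its SD. For a paired t-test the noncentrality is 0.56 × √n, which is 0.56 × √28 = 2.96 at n = 28. The exact noncentral t gives power 0.815 at 28 and 0.7998 at 27. The plan's 28 is reproduced, for the contrast between the two arms as they are defined.

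**2. What the pairs can estimate.** Let D be the device effect, R1 the effect of intraosseous versus infiltration, and R2 the effect of intraosseous versus block, assumed additive.

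- A maxillary pair estimates D + R1.
- A mandibular pair estimates D + R2.

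That is two estimable quantities for three unknowns at any jaw split, or one for two unknowns if all children are in one jaw. A difference of 0.56 SD fits D = 0.56 with R = 0 exactly as well as D = 0 with R = 0.56. D + R1 and D + R2 themselves, the whole-technique effects, are fully estimable.

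**3. What separating the device would take.** That would need a different trial with the route held fixed. With the SD of differences set to 1, 80% power and a two-sided 0.05 level, the number of pairs depends on how much of the 0.56 is due to the device:

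| Share due to device (assumed) | Device effect | Pairs needed |
|---|---|---|
| 75% | 0.42 | 47 |
| 50% | 0.28 | 103 |
| 25% | 0.14 | 403 |

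**4. How far the jaw mix could matter.** The documents give neither a split nor effects by jaw, so this is illustration only. With effects of 0.20 against infiltration and 0.92 against block, and a mandibular share s, the pooled effect is (1 − s) × 0.20 + s × 0.92. That is 0.38 at s = 0.25, 0.56 at s = 0.50 and 0.74 at s = 0.75. If the two effects are equal, the mix has no influence. Since jaw is constant within a child on my reading, it cannot bias a pair. It only determines what is being averaged.

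**5. What by-jaw estimates would show.** The 95% half-width in SD units is t(0.975, m − 1)/√m for m children.

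| m | Half-width | Interval around 0.56 |
|---|---|---|
| 8 | 0.84 | −0.28 to 1.40 |
| 14 | 0.58 | −0.02 to 1.14 |
| 20 | 0.47 | 0.09 to 1.03 |
| 28 | 0.39 | 0.17 to 0.95 |

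A test of whether the effect differs by jaw reaches 80% power only for a difference of about 1.10 SD at a 14/14 split, or 1.27 SD at 7/21. Both exceed the whole planned effect.

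**The case for a change.** The strongest case for a change is that the fault cannot be repaired by analysis. Readers carry away titles and conclusions, this title leaves out the route, and the remedy costs one sentence and two table rows from data already collected. Per-jaw counts alone would tell a reader which control procedure dominates.

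The non-separability stands in full, and so does the value of naming the route when the result is reported. The rest is weaker. The title is an abbreviation, and the arm definitions that govern the trial name both device and route. With no aims or conclusion section in the document, no one is shown to have credited the device alone.

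The case for by-jaw intervals is weaker still. They would not separate device from route. At this size they could not show that the jaws agree or differ, and two wide intervals invite the misreading that the technique works in one jaw only. With no primary pain outcome or time point named, the measure for those rows could be picked after the data are seen.

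Nor does silence in a short list of tests show that results by jaw are not intended. The independent-samples tests listed there would naturally serve factors that vary between children, of which jaw is one, although the document does not say so.

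**Conclusion.** The observation is correct but calls for no change. In 28 of 28 planned pairs the device and the route differ together, so the trial answers a question about whole techniques: computer-controlled intraosseous anesthesia against syringe infiltration or block. That is a legitimate question. The arm definitions state it, the order of methods is randomized within child, and 28 pairs give power 0.815 for the effect assumed. Comparing the techniques as packages is a fair trade-off; isolating the device would be a different trial, of 47 to 403 pairs under the shares assumed above.

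Pooling over jaws does not bias the within-child difference, and no harm from it can be quantified because the jaw split is not given. By-jaw intervals would have a half-width of 0.58 SD at an assumed 14 per jaw, which is too wide to be informative. In writing up, a careful analyst will name both arms in full and give the number of children per jaw.

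This rests on a two-sided test, on 0.56 being in units of the SD of within-child differences, on complete pairs, and on both teeth of a child lying in one jaw. The control needle and volume are not separately stated, so whether they differ too cannot be judged. If they do, they are part of the same package and the conclusion is unchanged.

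### The described envelope-and-card procedure does not guarantee a random, unpredictable pairing of molar and anaesthesia method

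*Combined protocol and SAP*

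**What the plan says.** Study Design describes a within-child comparison: "The study was conducted using a split-mouth design with 28 patients and 56 teeth". It also says "The patients included in the study were randomly assigned to two groups", although each child is meant to receive both methods, one on each side.

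Dental Anesthesia Methods gives the mechanism, in two steps.

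- **Method.** "The anesthesia method to be used in the first session was determined by randomization", and for this "each patient was asked to randomly select one of the envelopes labeled with different anesthesia methods".
- **Tooth.** In a sentence introduced only as an addition, "to determine which tooth to begin treatment on, patients were asked to choose between blue and green cards". The rule is fixed: "children who selected the blue card started with the right first molar, while those who selected the green card started with the left first molar".

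The second session takes the other method and the other molar by implication of the design. The same section adds: "All procedures were performed by the same dentist in a single-unit room".

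Study Design grades teeth by MIH-TNI, with category 2 taken as without hypersensitivity and category 4 as with it. The grade is not used to restrict or stratify allocation.

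The documents do not describe a generated sequence, opaque, sealed or numbered envelopes, anyone independent holding them, whether a used envelope goes back, or whether the method is known when the card is chosen.

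**The concern.** In a split-mouth trial the allocation that matters is which of a child's two molars gets which method. Here method order and first tooth fix that pairing jointly. Both are picks by the child, and nothing written protects either one from being seen, guided or repeated.

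A child's two molars may differ, most obviously in hypersensitivity, which plausibly affects pain. If the harder molar went more often to one method, the difference between teeth would be read as a difference between methods. The paired tests in Statistical Analysis remove differences between children. They do not remove a systematic difference between the two teeth of a child. Protection against that comes only from an unpredictable tooth-to-method assignment, which the wording about random assignment claims but the described procedure does not secure.

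**Working it through.** **Step 1. The plan's own figure.** Inputs from Determination of Sample Size: effect size 0.56, power 80%, 28 patients. The 5% level is from Statistical Analysis. I assume a two-sided paired t-test with 0.56 as the standardised paired difference. The noncentrality is 0.56 × √28 = 2.96 on 27 degrees of freedom, and power is 81.5%; at n = 27 it is 79.98%. So 28 reproduces and is not in dispute.

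**Step 2. How the two draws set the pairing.** Let p be the probability that the computer-controlled method comes first. Let q1 and q0 be the probabilities that the right molar is treated first when the computer-controlled or the conventional method comes first. Then

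P(right molar gets computer-controlled) = p·q1 + (1 − p)·(1 − q0).

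| Situation | p | q1 | q0 | Result |
|---|---|---|---|---|
| Fair method draw, 70% choose blue | 0.5 | 0.7 | 0.7 | 0.50 |
| Fair method draw, 90% choose blue | 0.5 | 0.9 | 0.9 | 0.50 |
| One method picked more often, 90% blue | 0.6 | 0.9 | 0.9 | 0.58 |
| One method picked more often, 90% blue | 0.7 | 0.9 | 0.9 | 0.66 |
| Card follows a known method, partly | 0.5 | 0.7 | 0.3 | 0.70 |
| Card follows a known method, strongly | 0.5 | 0.9 | 0.1 | 0.90 |
| Card follows a known method, always | 0.5 | 1 | 0 | 1.00 |

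For example, the second row is 0.5 × 0.9 + 0.5 × 0.1 = 0.50, and the fourth is 0.7 × 0.9 + 0.3 × 0.1 = 0.66. A fair method draw, independent of the card, absorbs any colour preference. An uneven method draw, or a card chosen with the method known, does not.

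**Step 3. What steering would cost.** The documents give no figures, so these inputs are assumptions:

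- q = share of children whose two molars differ in hypersensitivity, 0.2 to 0.5;
- f = share of those children in whom the harder molar is steered to the same method, 0.25 to 0.5, with the rest falling evenly;
- g = shift in the paired difference caused by hypersensitivity, in SD of that difference, 0.5 or 1.

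Bias = q × f × g. The rejection probability with no true method effect comes from the noncentral t with noncentrality bias × √28 on 27 degrees of freedom, two-sided 5%.

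| g | q | f | Bias (SD) | Noncentrality | Error rate |
|---|---|---|---|---|---|
| any | any | 0 | 0 | 0 | 5.0% |
| 0.5 | 0.2 | 0.25 | 0.025 | 0.13 | 5.2% |
| 0.5 | 0.5 | 0.5 | 0.125 | 0.66 | 9.8% |
| 1 | 0.2 | 0.25 | 0.05 | 0.26 | 5.7% |
| 1 | 0.5 | 0.5 | 0.25 | 1.32 | 24.8% |

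Against the planned effect, the largest bias is 0.125/0.56 = 22% at g = 0.5 and 0.25/0.56 = 45% at g = 1. The top figure also depends on scale: if 1 SD means the residual SD, discordant pairs widen the spread, and simulation gives about 19% instead of 24.8%.

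**The case against.** The section says the method was randomised and that the child selected at random. *Labeled* may loosely describe closed envelopes with the method inside; a random pick makes little sense if the method can be read. The colour card is harmless under a fair, concealed and independent draw, as step 2 confirms. The error rates rest wholly on assumed inputs, and a 1 SD effect is nearly twice the planned 0.56. Eligibility also requires deep caries treatable with vital pulp therapy and no history of acute pain, which narrows the differences between a child's molars.

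All of this stands, and it rules out several stronger readings that a reader might infer:

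- *The allocation was unconcealed.* The wording suggests it, but does not prove that the envelopes were readable.
- *The method was known when the cards were offered.* The sentence order suggests it, but the linking words fix no time order.
- *The dentist steered the pairing.* The child makes both picks. A single operator does not imply control of the draw, and nothing shows that steering occurred.
- *The colour choice by itself makes the pairing non-random.* Step 2 shows that it does not.

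What remains is that even with closed envelopes the generation, sealing, custody, logging and order of the draws are unstated, and no other section supplies them. The protection is therefore not secured on either reading.

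**Conclusion.** The point holds as a weakness of the stated procedure, not as evidence of bias. Random and unpredictable pairing of tooth and method depends on conditions that the documents do not state: a fair method draw, concealed, and independent of the card.

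The size is conditional. With no steering, the bias is zero and the error rate is 5%. Under the assumed shares of discordant and steered children, the error rate is 5.2%-9.8% for a 0.5 SD effect of hypersensitivity and 5.7%-25% for 1 SD. The upper end should be read as an extreme of the illustration. The sample size of 28 is unaffected. The change is worth making because it protects the main comparison at almost no cost.

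**What to change.** Replace both picks with one computer-generated list over the four sequences (method first × side first), 7 children each: 4 × 7 = 28. Use either a single random permutation of the 28 or permuted blocks whose size is undisclosed or varied. Fixed blocks of four would let anyone who sees each allocation deduce the last one in the block. Someone who does not treat the children should prepare the list and place it in opaque, sealed, sequentially numbered envelopes with no method on the outside. Open the next envelope only after enrolment and MIH-TNI grading of both molars, and log its number and date.

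The cost is about an hour to make the list and 28 envelopes, with no extra patients, visits or procedures. A small downside is that the child no longer determines the order; a card with no effect on allocation could be kept for engagement.

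The text is in the past tense, so the trial may already have been carried out. For children treated under the current procedure, report exactly how envelopes and cards were used and in what order. Give counts of method by side, by session and by MIH-TNI category, and limit the statement about random assignment to what was actually done.

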Statistical Analysis: Data were analyzed using IBM SPSS version 23. The normality of data distribution was assessed with the Shapiro–Wilk test. For normally distributed data, parametric tests (Independent Samples t-test, Paired Samples t-test, Repeated Measures ANOVA, Pearson correlation) were used; for non-normally distributed data, non-parametric tests (Mann–Whitney U test, Wilcoxon test, Friedman test, Spearman's rho) were applied. For categorical variables, Fisher's Exact test (with Monte Carlo correction), Marginal Homogeneity test, and Cochran's Q test were used. Quantitative data were presented as mean \pm standard deviation or median (min–max), while categorical data were expressed as frequency and percentage. A p-value of < 0.05 was considered statistically significant.
